8.1 Personnel training

Prior to enrollment of the first subject in the study protocol, the PI will ensure that staff has completed appropriate training and that all documentation including IRB approval is completed and available. The purpose of training is to ensure that study personnel are carrying out the protocol in a consistent way and are adhering to good clinical practice guidelines. Staff will have current Human Subjects Training Certification on file at the IRB office. Before enrollment begins, study coordinators and research assistants who will perform the outcome assessments will be trained in all procedures, including completion of case-report forms (CRFs).

The PI and research staff will constitute the first line of monitoring of the safety of the human participants. Surveillance for AEs will consist of questioning subjects about potential AEs at every study contact, having subjects report any adverse event to the study team, and having subjects undergo vital sign checks and physical exams during each study visit. Laboratories will be performed and checked at screening before enrolling the subject in the study.

All study personnel are required to read the consent form and the protocol.

8.2 Data quality

The PI will perform continuous monitoring of data quality and completion of CRFs. The PI will review database forms and source documents to ensure that the information on the forms is complete and consistent with the source documents.

Chapter 9. Participant Safety and Confidentiality

9.1 Consent

Consent will be obtained for enrollment from participants. For each consent process, study personnel will discuss the details of the study, the risks and benefits, and the subject's rights and responsibilities if they choose to participate in the trial and their right to refuse to participate. It will be made clear that their clinical care will not be affected by their decision.

9.2 Institutional Review Board process

IRB approval must be obtained and on file before enrolling participants into the clinical trial.

9.3 Laboratory values

The following clinical laboratory tests will be measured at screening (or baseline for known postmenopausal women) and nine week visits and as clinically indicated.

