- Initiation of PAH therapy (prostacyclin analogues or receptor agonists, endothelin-1 receptor antagonists, phosphodiesterase-5 inhibitors, soluble guanylate cyclase stimulators) within three months of enrollment; the dose must be stable for at least 3 months prior to Baseline Visit. PAH therapy which is stopped and then restarted or has dose changes which are not related to initiation and uptitration will be allowed within 3 months prior to the Baseline Visit.
- Hormone therapy.
- Use of warfarin or other anticoagulant (use of aspirin is permitted).
- Platelet count <100,000.
- Renal failure (creatinine \geq 2.0).
- Child-Pugh Class C cirrhosis.
- Current or recent (< 6 months) chronic heavy alcohol consumption.
- Current use of another investigational drug (non-FDA approved) for PAH.

ENDPOINTS:

- Changes in right ventricular systolic pressure, right ventricular fractional area, stroke volume index and tricuspid annular plane systolic excursion
- Changes in six-minute walk distance
- Changes in plasma NT-proBNP and estradiol levels
- Assess safety and side effects associated with fulvestrant administration in subjects with pulmonary arterial hypertension

STUDY OBSERVATIONS:

- Subjects will be evaluated in person at screening, baseline, two weeks, four weeks, eight weeks and nine weeks.
- Subjects will have telephone follow-up at week twelve.
- Laboratory tests including a complete blood count, hepatic function panel, follicle-stimulating hormone, coagulation studies (PT/INR) will be performed at the screening visit.
- Research laboratories such as estradiol (E2) and NT-proBNP levels will be evaluated at baseline and repeated after nine weeks of fulvestrant administration.
- Subjects will have six minute walk testing at baseline and week nine.
- Subjects will have a transthoracic echocardiogram at screening or baseline and week nine.

SAMPLE SIZE AND POWER:

A total of 5 subjects will be enrolled to receive fulvestrant at baseline, two weeks, four weeks, and eight weeks. Formal power calculations were not performed as this study is intended to show feasibility and for hypothesis-generation.

DATA ANALYSIS:

The study endpoints will be evaluated using summary statistics and graphical tools. Univariate analysis will be performed for all variables of interest. These will be carried out by comparing the changes from baseline using signed rank tests for continuous variables and McNemar's test for categorical variables.

Brief Table of Contents

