5.1.6 Visit 5 (Nine weeks -3 or + 7 days)

The research coordinator will call the subject 1-2 days before the visit as a reminder. The coordinator will instruct the subject to not eat or drink (except water) and to avoid heavy exercise for 12 hours before the study day assessment. Subjects will be instructed

to bring a list of the current medications and to take all medications before the visit other than any oral PAH medication(s). The subject should bring their oral PAH medication(s) with them to be taken after the blood draw. The subject will be reminded to wear appropriate clothing and shoes to complete a 6MWT.

The subject will arrive at the study site outpatient clinic. The following procedures will be performed:

- Labs/Phlebotomy: research labs
- Echocardiogram
- Interim medical history
- Assess any adverse events/serious adverse events
- Vital signs
- Review current medications
- WHO functional class assessment
- Physical exam
- 6MWT with Borg scores

There is no particular order in which these procedures must be done, but it is recommended that the fasting blood draw be performed first.

Blood samples for study assays will be processed and banked. After obtaining the blood samples, the subject will be instructed to take their regular medications.

Echocardiography will be performed. The investigator or research nurse will take a history and perform a physical examination. The subject will complete the 6MWT.

The research coordinator will thank the subject for their participation in the clinic visits of the clinical trial. A follow-up phone call will be scheduled.

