5.2 Study schedule of procedures

The table below summarizes the study procedures.

Table 1. Study Procedures

	Screening*	Baseline	Week 2	Week 4	Week 8	Week 9	Week 12 Follow-up Phone Call
Visit #		1	2	3	4	5	
Day#	-28 - 0	-2 - 0	14 ± 3	28 ± 3	56 ± 3	- 3- (63) + 7	84 ± 3
Informed consent	X						
General Testing							
Physical Exam		X		X		X	
Medical history	X	X ^a					
Vital signs	X	X	X	X	X	X	
WHO FC Assessment		X		X		X	
Laboratory Test							
Complete blood count	X	X ^a					
Hepatic function panel	X	X ^a					
Coagulation studies (PT/INR)	X	X ^a					
FSH	X	X ^a					
Research labs		X				X	
Study procedures							
Study drug administration		X	X	X	X		
Echocardiogram	X	X ^a				X	
Six minute walk test		X				X	
Concomitant Medications	X	X	X	X	X	X	X
Assess Adverse Events/Serious Adverse Events		X	X	X	X	X	X

X^a: Only to be performed if not done at screening visit. These assessments should be reviewed by the PI prior to first administration of study drug to ensure that the subject meets inclusions/exclusion criteria.

*Screening Visit procedures may be done at the Baseline Visit for female participants who are known to be post-menopausal: (1) > 50 years old and have not menstruated during the preceding 12 months or (2) have undergone bilateral oophorectomy. Review of medical history, medications, and informed consent must be obtained prior to the combined visit.

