9.3.1 Hematology

Complete blood count will be performed at screening.

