9.3.2 Hepatic function panel

Hepatic function panel will be performed at screening.

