9.3.3 Coagulation studies

Prothrombin time, INR will be performed at screening.

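### Section 9.3 places the clinical laboratory tests at week 9, but Visit 5 and Table 1 do not; staff who follow the schedule would draw no routine post-dose hepatic panel or blood count

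*Combined protocol and SAP*

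**What the plan says.** The lead sentence of section 9.3 gives the timing of the clinical laboratory tests: "The following clinical laboratory tests will be measured at screening (or baseline for known postmenopausal women) and nine week visits and as clinically indicated". Its subsections then mention screening alone: "Complete blood count will be performed at screening" (9.3.1), "Hepatic function panel will be performed at screening" (9.3.2) and "Prothrombin time, INR will be performed at screening" (9.3.3). Section 9.3.4 does the same for FSH.

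At week 9, the laboratory line of Visit 5 (5.1.6) reads "Labs/Phlebotomy: research labs" and names no clinical test. In Table 1 (5.2), blood count, hepatic panel, PT/INR and FSH are marked at screening, and at baseline with the footnote "Only to be performed if not done at screening visit". Their later cells are empty. The only laboratory row marked at week 9 is research labs.

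The Protocol Summary treats the two groups separately. On the clinical tests it says "Laboratory tests including a complete blood count, hepatic function panel, follicle-stimulating hormone, coagulation studies (PT/INR) will be performed at the screening visit". On the research tests it says "Research laboratories such as estradiol (E2) and NT-proBNP levels will be evaluated at baseline and repeated after nine weeks of fulvestrant administration".

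Section 5.1.8 gives early-withdrawal subjects the Visit 5 procedures. Section 9.6.5 allows clinical laboratories after permanent withdrawal of treatment, but only if they are needed.

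**The concern.** Two current texts give different instructions for the same visit, and no rule of precedence settles which applies. Coordinators usually work from visit lists and the schedule table, and here both omit the tests.

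The hepatic panel matters most. Section 9.8 places raised liver enzymes among the fulvestrant effects seen in more than 10%, and section 4.1 admits patients with Child-Pugh Class B disease at 250 mg. Section 9.6.3 makes a qualifying laboratory abnormality an adverse event, section 7.7 promises the incidence and grade of toxicities, and safety is part of Aim 4 (2.2). An enzyme rise without symptoms cannot be found by history, vital signs or examination. If no blood is tested, the report would show no such events, and that could be read as evidence of hepatic safety. The blood count has a weaker but similar rationale: 9.8 lists leukopenia below 1%.

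**Working it through.** The plan states no figure on this point, so the check compares the texts and counts scheduled tests.

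**Step 1. The texts side by side**

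| Place | Screening or baseline | Week 9 |
|---|---|---|
| 9.3, lead sentence | clinical tests | clinical tests |
| 9.3.1 to 9.3.4 | clinical tests (screening) | not mentioned |
| Summary, Study Observations | clinical tests (screening) | research labs only |
| 5.1.6, Visit 5 | – | research labs only |
| Table 1 | clinical tests | research labs only |
| 5.1.8, early withdrawal | – | as Visit 5 |

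The empty week-9 cells are unlikely to be a table-reading fault, because the Visit 5 list agrees with them independently. Nor does the research-labs line cover the clinical tests. The baseline list in 5.1.2 gives research labs as estradiol, NT-proBNP, progenitor cells and other research assays, and its footnote adds the screening labs only for a combined visit.

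**Step 2. Scheduled post-dose tests (week 2 to week 12)**

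- Under Table 1 and the visit lists: hepatic panel 0, blood count 0, PT/INR 0, FSH 0, research labs 1 per subject.
- Under the lead sentence of 9.3: hepatic panel 1 and blood count 1 per subject.
- For the 5 planned subjects: 5 × 0 = 0 against 5 × 1 = 5 of each test. Replacements would add to this.

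**Step 3. Timing**

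Inputs from Table 1: screening day −28 to 0; fourth dose day 56 ± 3 (53 to 59); Visit 5 day 63, −3 or +7 (60 to 70); week-12 call day 84 ± 3 (81 to 87).

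- Last scheduled panel to Visit 5: 63 − 0 = 63 to 63 + 28 = 91 days. With the Visit 5 window: 60 − 0 = 60 to 70 + 28 = 98 days.
- Fourth dose to a Visit 5 panel: 63 − 56 = 7 days (60 − 59 = 1 to 70 − 53 = 17).
- Visit 5 panel to the week-12 call: 84 − 63 = 21 days (81 − 70 = 11 to 87 − 60 = 27).

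A week-9 panel would thus come after all four doses. It would leave a nominal three weeks before the adverse-event reporting period ends at week 12 (9.6.3).

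**Step 4. Other routes to a post-dose laboratory value**

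Two texts mention one: 9.3, when clinically indicated, and 9.6.5, if needed after permanent withdrawal of treatment. Both depend on someone having a reason to test. The week-12 call (5.1.7) brings a worsened subject in for evaluation but does not mention laboratory tests.

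**The case against.** The strongest reply is that the phrase about nine-week visits in 9.3 may itself be the slip. It stands alone against Visit 5, Table 1, the Summary and the four subsections directly below it. Deleting it and justifying the absence of scheduled post-dose tests would also make the protocol consistent. This stands as far as it goes: the documents do not show that 9.3 governs, and a reader who infers that the schedule breaches a settled requirement goes too far. The case for week 9 rests on safety. Section 5.1.2 gives it some support, since it uses the screening safety labs as baseline values, and these have limited use with no later value.

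A second reply is that 9.3 cannot justify repeating everything it covers. This is also right. FSH serves to establish menopausal status and has no evident use at week 9. Section 9.8 lists no PT/INR change, and the plan's bleeding and anticoagulant provisions concern eligibility and caution. Only the hepatic panel has a strong rationale in the documents, with the blood count second.

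A third reply is that the consequence is small. The trial is an uncontrolled feasibility study of 5 women, the panel would follow the last dose, and adverse events are assessed at every visit from baseline and at the week-12 call. That limits the gap to laboratory effects but does not close it. A reader might infer that post-dose safety is unmonitored, or that no post-dose laboratory value can be obtained; neither is so.

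Section 8.1 is not part of the conflict. It describes the check before enrolment and stays true under either reading.

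**Conclusion.** The inconsistency is certain and lies in current text. Its size is 0 scheduled post-dose hepatic panels or blood counts per subject if 5.1.6 and Table 1 are followed, against 1 of each under 9.3. This assumes that staff work from the visit list and the schedule; if they act on 9.3, the gap does not arise. Efficacy analyses and sample size are unaffected. The correction should be made because a known common laboratory effect could otherwise be missing from the toxicity summary in 7.7.

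A reader might go on to infer a chance that the trial overlooks a case. With an assumed rate of exactly 10%, the chance of at least one enzyme rise among 5 subjects is 1 − 0.90^5 = 0.41. The documents do not support using this as a probability of a missed event. They give only a lower bound on the rate, and they do not say how many rises are symptomless or how many would be present at week 9.

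**What to change.** - In 5.1.6, extend the laboratory line to research labs plus hepatic function panel (first priority) and complete blood count. Mark those two rows at week 9 in Table 1. The early-withdrawal visit (5.1.8) then inherits them without further change.
- Align 9.3.1, 9.3.2 and the Summary to screening (or baseline) and week 9.
- State in 9.3 that FSH is not repeated, and that PT/INR is repeated only if the sponsor intends it. If so, add it to the same places and to 9.3.3.
- Leave 8.1 as it is.

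The cost is a short amendment and 2 tests × 5 subjects = 10 routine tests, plus those for any replacements, on a blood draw already scheduled. The benefit has limits: the panel falls after the day-56 dose, so it serves detection and safety reporting and cannot guide dosing, and a single panel may miss a rise that has already resolved.

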9.3.1 Hematology

Complete blood count will be performed at screening.

9.3.2 Hepatic function panel

Hepatic function panel will be performed at screening.

9.3.3 Coagulation studies

Prothrombin time, INR will be performed at screening.

9.3.4 Follicle-stimulating hormone

FSH will be performed at screening.

9.4 Fulvestrant-related laboratory abnormalities and drug interactions

Hypersensitivity reactions including urticarial and angioedema have been reported. Use of fulvestrant in patients with a history of bleeding disorders (including thrombocytopenia) should be approached with caution. Subjects on anticoagulant therapy will not be enrolled in the study. Aspirin is permitted as a concomitant medication. Subjects with moderate hepatic impairment will be given a lower dose of fulvestrant.

9.5 Other events

We will not discontinue study drug for clinical events not thought to be serious drug-related AEs. For example, a hospitalization for clinical worsening will not result in cessation of trial participation. Such events could result in missing data for primary and secondary endpoints, comprising the integrity of the analysis. As the trial does not prohibit any therapies which is the standard of care in PAH, there is no ethical or safety reason to stop trial participation under such circumstances. Even if subjects are withdrawn from the study drug outcome assessments will continue. Subjects who are not compliant or stop the treatment portion of the study will be replaced.

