3.2.2 Exclusion criteria

- Age < 18 years
- Treatment with estrogen or anti-hormone therapy (tamoxifen, anastrozole, etc.)
- WHO Class IV functional status.
- History of breast cancer.
- Clinically significant untreated sleep apnea diagnosed by polysomnography.

- Left-sided valvular disease (more than moderate mitral valve stenosis or insufficiency or aortic stenosis or insufficiency), pulmonary artery or valve stenosis, or ejection fraction < 45% on echocardiography.
- Initiation of PAH therapy (prostacyclin analogues or receptor agonists, endothelin-1 receptor antagonists, phosphodiesterase-5 inhibitors, soluble guanylate cyclase stimulators) within three months of enrollment; the dose must be stable for at least 3 months prior to Baseline Visit. PAH therapy which is stopped and then restarted or has dose changes which are not related to initiation and up-titration will be allowed within 3 months prior to the Baseline Visit.
- Hospitalized or acutely ill.
- Use of warfarin or other anticoagulant (use of aspirin is permitted).
- Platelet count <100,000.
- History of bleeding disorder.
- Renal failure (creatinine \geq 2.0).
- Child-Pugh Class C cirrhosis.
- Current or recent (< 6 months) chronic heavy alcohol consumption.
- Current use of another investigational drug (non-FDA approved) for PAH.

Chapter 4. Treatment

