5.1.2 Study Day – Visit 1 (Baseline), Day 0 (– 2 days)

The research coordinator will call the subject 1-2 days before the visit as a reminder to not eat or drink (except water) and to avoid heavy exercise for 12 hours before the study day assessment. Subjects will be instructed to bring a list of the current medications and to take all medications before the visit other than any oral PAH medication(s). The subject should bring her oral PAH medication(s) with her to be taken

after the blood draw. The subject will be reminded to wear appropriate clothing and shoes to complete a 6MWT.

Baseline information will be used to characterize the participants. Safety laboratories obtained at the screening visit will be used as baseline measurements. All baseline data will be collected prior to study drug administration. If a combined Screening Visit and Baseline Visit is performed, all labs (other than FSH for female subjects who are known to be post-menopausal per inclusion criteria) must be confirmed and all inclusion/exclusion criteria must be met prior to study drug administration.

The subject will arrive at the study site outpatient clinic. The following procedures will be performed:

- Vital signs
- Labs/Phlebotomy: estradiol level, NT-proBNP, hematopoietic progenitor cells (EPCs), and other research labs*
- Echocardiography
- Interim medical history
- Review current medications
- WHO functional class assessment (must be done by a study physician or research nurse)
- Physical exam
- Six minute walk testing (6MWT) with Borg scores
- Assess any adverse events (AEs) or serious adverse events (SAEs) that have occurred since last visit
- Review of inclusion/exclusion criteria
- Administration of study drug, fulvestrant, by the study physician or research nurse
- Reinforce instructions on recording of new medications and dose changes

*Screening labs should be drawn if performing a combination baseline/screening visit. All screening laboratory tests must be received and all inclusion/exclusion criteria confirmed by the PI before the subject can receive study drug.

There is no particular order in which these procedures must be done EXCEPT for the administration of the study drug, which should be performed last and only if the subject is eligible per inclusion/exclusion criteria.

Blood samples for research study assays will be kept a room temperature and shipped to be processed as well as processed on site and banked in a freezer at -70° C.

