5.1.3 Visit 2, Week 2 (Two weeks ± 3 days)

The research coordinator will call the subject 1-2 days before the visit as a reminder. Subjects will be instructed to bring a list of the current medications and to take all medications before the visit.

The subject will arrive at the study site outpatient clinic. The following procedures will be performed:

- Interim medical history
- Assess any AEs/SAEs
- Vital signs
- Review current medications
- Study drug administration by study physician or research nurse
- Reinforce instructions on recording of new medications

The study medication will be administered last by the research nurse or a study physician. It will be administered according to the manufacturer's instructions. 500 mg will be given as two intramuscular injections to eligible subjects who do not have Child-Pugh Class B liver disease and 250 mg for eligible subjects who have Child-Pugh Class B liver disease. Each syringe holds 250 mg of fulvestrant.

The research coordinator will thank the subject for their attendance, schedule the next visit and reinforce compliance with the study visit timeline.

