5.1.5 Visit 4, Week 8 (Eight weeks \pm 3 days)

The research coordinator will call the subject 1-2 days before the visit as a reminder. Subjects will be instructed to bring a list of the current medications and to take all medications before the visit.

The subject will arrive at the study site outpatient clinic. The following procedures will be performed:

- Interim medical history
- Assess any adverse events/serious adverse events
- Vital signs
- Review current medications
- Study drug administration by study physician or research nurse
- Reinforce instructions on recording of new medications

The study medication will be administered last by the research nurse or physician. It will be administered according to the manufacturer's instructions. 500 mg will be given as two intramuscular injections to eligible subjects who do not have Child-Pugh Class B liver disease and 250 mg for eligible subjects who have Child-Pugh Class B liver disease. Each syringe holds 250 mg of fulvestrant.

The research coordinator will thank the subject for their attendance, schedule the final study visit and reinforce compliance with the study visit timeline.

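### An anticoagulant bars entry and the first dose, but no stated rule holds the day 14, 28 or 56 injections if one is started on study

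*Combined protocol and SAP*

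**What the plan says.** **Entry and dose 1.** Section 3.2.2 lists as an exclusion "Use of warfarin or other anticoagulant (use of aspirin is permitted"). Section 9.4 repeats it as an enrolment rule, "Subjects on anticoagulant therapy will not be enrolled in the study", straight after advising caution in bleeding disorders. It then allows aspirin alongside the study drug. Section 5.1.2 puts the first injection at the end of the visit, "which should be performed last and only if the subject is eligible per inclusion/exclusion criteria", and requires the investigator to confirm all criteria beforehand.

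**Doses 2 to 4.** Sections 5.1.3 to 5.1.5 list a review of current medications and then the injection. The drug comes at the end ("The study medication will be administered last by the research nurse or physician") and follows the label ("It will be administered according to the manufacturer's instructions"). No eligibility review is listed at these visits. The only condition that changes a dose is Child-Pugh Class B liver disease.

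**Continuing or stopping.** Section 9.5 says "We will not discontinue study drug for clinical events not thought to be serious drug-related AEs". It gives hospitalization for worsening as its example and, because the trial forbids no standard PAH therapy, adds that "there is no ethical or safety reason to stop trial participation under such circumstances". Section 9.6.5 keeps subjects on drug if they worsen clinically, but lets the investigator withdraw a subject for concurrent illness, adverse events or other reasons of her welfare. It names one on-study change that stops the drug with assessments kept: developing an indication for fulvestrant, such as breast cancer.

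**Other medication.** Section 4.2 leaves PAH medication unconstrained and is silent on anticoagulants.

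**The concern.** The bleeding concern is the protocol's own. Anticoagulant use, a history of bleeding disorder and platelets under 100,000 are all exclusions for a drug given as 5 mL injections into the buttock. The protection is written for the first dosing day only.

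Take a woman hospitalized in week 3 for worsening judged unrelated to the drug, who goes home on an anticoagulant. She could not have received dose 1 in that state. The medication review at week 4 should show the new drug, yet nothing tells the research nurse or physician to withhold the injection at week 4 or week 8. The continuation rules in 9.5 and 9.6.5 cover the event that brought her to hospital and give no cue to pause. Her safety at those visits rests on someone choosing to step in.

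**Working it through.** The plan gives no figure on this point. The check is a comparison of provisions and a count of dosing days.

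**1. Is there a stated hold after dose 1?**

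| Provision | Bears on a new anticoagulant? | Requires a hold? |
|---|---|---|
| 3.2.2 and 9.4, enrolment bar | Yes, by name | At entry only |
| 5.1.2, eligibility confirmed before injection | Yes, through the criteria | Dose 1 only |
| 5.1.3 to 5.1.5, medication review | Would probably reveal it | No action attached |
| 5.1.3 to 5.1.5, dosing of eligible subjects | Possibly | No later eligibility check listed; the same sentence is used at baseline to separate the two doses |
| 5.1.3 to 5.1.5, manufacturer's instructions | Unknown; not among the documents | None stated |
| 9.4, aspirin allowed alongside | By implication | No |
| 9.3, tests at screening and \"nine week visits and as clinically indicated\" | Allows an unscheduled test | No; week 9 falls after the last dose |
| 9.5 and 9.6.5, continuation rules | Not addressed | No |
| 9.6.5, investigator's right to withdraw | Covers it | Permits, does not require |
| 9.10, other medications not to be used | Names hormone therapy only | No |

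No row requires a hold on days 14, 28 or 56.

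**2. How much dosing is uncovered?** Inputs from section 4.1: dosing days 0, 14, 28 and 56; two 5 mL injections per day at 500 mg, or one at 250 mg for Child-Pugh Class B.

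- Dosing days after the entry check: 4 − 1 = 3 of 4.
- At 500 mg: 3 × 2 = 6 of 4 × 2 = 8 injections, or 6 × 5 = 30 of 8 × 5 = 40 mL.
- At 250 mg: 3 of 4 injections, or 3 × 5 = 15 of 4 × 5 = 20 mL.

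The count for one woman depends on when the anticoagulant starts, assuming that she stays on it:

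| Start | Dosing days left | Injections at 500 mg | Injections at 250 mg |
|---|---|---|---|
| Between doses 1 and 2 | 3 | 6 | 3 |
| Between doses 2 and 3 | 2 | 4 | 2 |
| Between doses 3 and 4 | 1 | 2 | 1 |
| After dose 4 | 0 | 0 | 0 |

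The woman in the week-3 example falls in the second row.

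**3. Where does continuation come from?** Section 9.5 governs stopping for clinical events, and the 9.6.5 sentence governs worsening. Starting a medicine is neither. Continuation therefore follows from the dosing schedule together with silence on anticoagulants. The two rules matter because they keep the woman on drug through the event that may have led to the prescription.

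**4. Is there a limit to that?** Yes. Section 9.8 lists blood clots as a risk of fulvestrant at under 1%. A serious clot thought to be drug-related falls outside the 9.5 continuation rule. A clot judged unrelated does not.

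**The case against.** The strongest reply is that the protocol does not intend anticoagulants on study and leaves room to act. Section 9.4 permits aspirin by name as an accompanying drug, which implies that anticoagulants are not permitted. The discretion in 9.6.5 is itself written and broad. Section 9.5 foresees subjects being taken off the drug. The label may cover the case. Medications and adverse events are reviewed before each injection in a five-subject, single-center study. All of this stands as evidence of intent and as a partial safeguard. None of it says that the injection must be held.

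It can also be said that low platelets and bleeding disorders are entry exclusions without an on-study hold, so anticoagulants are being singled out. That is fair. The practical difference is that a new anticoagulant can be found at a review already scheduled before every dose, with no added test.

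Three stronger readings are tempting and are not supported:

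- *Section 9.5 directs staff to inject an anticoagulated woman.* It does not. It concerns clinical events, and its remark about ethics and safety rests on standard PAH therapy being allowed. It makes no claim about injecting under anticoagulation.
- *Section 4.2 permits anticoagulants on study.* It frees PAH medication only.
- *Three quarters of the trial's injections are at risk.* For five subjects at 500 mg, 5 × 6 = 30 of 5 × 8 = 40 injections follow the entry check, but that only restates the schedule. It would be exposure only if all five started an anticoagulant before dose 2 and stayed on it.

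**Conclusion.** The gap is real: a condition that bars dose 1 has no stated consequence at doses 2 to 4. Up to 3 of 4 dosing days per affected subject are uncovered, fewer if the anticoagulant starts later.

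The conclusion rests on the text as supplied. It assumes that the manufacturer's instructions, which cannot be seen here, do not already impose a hold. The documents give no rate of anticoagulant starts and no rate of injection bleeding, so neither the probability nor the size of harm can be stated. With five subjects the situation may never arise. It is a safety omission that should be corrected because the correction is specific and cheap. It does not invalidate the design, and it does not show that the investigator would in fact dose such a woman.

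**What to change.** 1. In 9.4, cross-referenced in 4.2, state that fulvestrant is not injected while a subject is on warfarin or another anticoagulant, aspirin excepted. A dose that cannot be given within its ±3-day window is skipped. The week-9 and week-12 assessments continue, as the protocol already requires after drug withdrawal.
2. In 5.1.3 to 5.1.5, require the existing medication review to check for a new anticoagulant before the injection and to refer any to the study physician.
3. In 9.5 and 9.6.5, add to the sentences that continue study drug: except as stated in 9.4.

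This follows the form of the rule that 9.6.5 already has for a new fulvestrant indication. It adds no visit or test, since medications are already reviewed and the drug is already given last. The cost is that a subject may miss a dose and be replaced under 7.3.1, 7.3.3 and 9.5, which means recruiting one more woman. The missed-dose subject's data would still enter the secondary analyses (7.3.1) and the safety analysis (7.7).
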